Primary objective: To test the efficacy of NMBR with sugammadex, compared to neostigmine, to reduce inadequate NMBR and its related hypoventilation during the immediate postoperative period after kidney transplantation surgery, after adjusting for qTOF recovery and morphine equivalents received. We define hypoventilation as the incidence of ≥ 1 minute-long events of MV $<40\%$ of expMV. Minute ventilation will be measured continuously with a noninvasive respiratory volume monitor for the first 3h after the end of surgery or until meeting discharge criteria from the post-anesthesia care unit (PACU) (if sooner than 3h).

Secondary objective: To test the efficacy of NMBR with sugammadex, compared to neostigmine, to reduce inadequate NMBR and its related hypoventilation during the first 3 postoperative days in patients after kidney transplantation surgery, after adjusting for qTOF recovery and morphine equivalents received. We define hypoventilation as the incidence of ≥ 1 minute-long events of MV $<40\%$ of expMV. Minute ventilation will be measured continuously with a noninvasive respiratory volume monitor for up to 3d after surgery or until meeting end of monitoring criteria (if sooner than 3d)

Additional secondary objectives: To test if NMBR with sugammadex, compared to neostigmine, reduces patient's reported dyspnea scores (with the validated Patient-Reported Outcomes Measurement Information System, PROMIS®, assessment), decreases postoperative pulmonary complications (PPCs)

possibly related to inadequate NMBR after kidney transplantation surgery (i.e. respiratory insufficiency, gastric aspiration, pneumonia), improves kidney graft outcomes and reduces hospital resources utilization (i.e. hospital length of stay, ICU admission) and estimated healthcare costs.

II. Background and Significance/Preliminary Studies:

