We have designed a prospective randomized double-blind single center study on 100 patients with severe kidney failure undergoing kidney transplantation surgery. Patients will be randomized to receive either NMB with rocuronium and sugammadex for NMBR (intervention group) or NMB with rocuronium and neostigmine for NMBR (control group). Respiratory function will be objectively monitored starting in PACU and during the first 3 postoperative days or until end of monitoring criteria are met. A blinded assessor will record the frequency of hypoventilation events as well as the accumulated minutes of hypoventilation. Quantitative TOF monitoring will be evaluated by a blinded investigator. Additional data related to patient's comorbidities, morphine equivalents (mg/kg) received, validated dyspnea patient-reported scores, pulmonary complications, kidney graft relevant data and outcomes, and hospital resource utilization and estimated costs will also be collected.

After signing informed consent, patients will be randomized to receive, during kidney transplant surgery, NMB with rocuronium and NMBR with either sugammadex (intervention group) or neostigmine (control group). Both groups will receive intraoperative NMB agents and reversal medications as guided by qTOF monitoring and following FDA-approved doses (see details below). In the PACU, we will perform continuous monitoring of their MV during their PACU stay and assess qTOF at selected time points in all patients. Institutional discharge criteria from PACU is based on an Aldrete's score[33] ≥ 8 assuming there are no discharge concerns by the patient's healthcare providers (PACU nurse, anesthesiologist and/or surgeon). After discharge from PACU and during the first 3 postoperative days (or until end of monitoring criteria if sooner) we will maintain the continuous MV monitoring and daily quantitative TOF assessment, collect opioids received and data relevant to pulmonary complications, kidney graft outcomes and estimated healthcare costs. At the postoperative surgery clinic visit or by phone interview we will collect patient's subjective dyspnea scores and compare to their baseline (with a validated questionnaire), as well as updated PPCs, kidney graft outcomes, hospital resources utilization and estimated healthcare costs.

Preoperative phase

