- NMBR brief protocol: The sugammadex (intervention) or neostigmine (control) will be administered at the end of the surgery. The goal will be to administer the appropriate NMBR medication when ≥ 2 twitches are objectivized with the qTOF monitor. NMBR drugs and dosing for each group will follow standard of care FDA-approved doses, as follows: Sugammadex 2 mg/kg will be administered when spontaneous recovery has reached the reappearance of the second twitch in response to TOF stimulation.

	Sugammadex dosing (mg/kg)	Neostigmine dosing (mg/kg)
T4 recovered	2	0.03-0.05 (max 5 mg)
T2/T3 recovered	2	0.05-0.07 (max 5 mg)
T0/T4 with 1-2 post-tetanic twitches present or T1 recovered	4 or wait	Wait

Overdosing of neostigmine will be avoided to prevent neostigmine-induced muscle weakness. Neostigmine will be administered simultaneously with the appropriate glycopyrrolate dose (0.2 mg per 1.0 mg of neostigmine).

Extubation will be performed following the usual standard of care criteria of adequate level of consciousness, presence of airway protection reflexes and spontaneous ventilation parameters in addition to quantitative TOF $T4/T1 >0.9$. The following times (minutes) will be recorded: NMBR administration-to-T4/T1 >0.9 , NMBR administration-to-extubation, total operating room time.

Postoperative in-hospital phase

The blinded investigator will collect the following study-related information:

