- The blinded investigator will assess the presence of residual NMB with the quantitative TOF monitor by calculating the average of 3 measurements of qTOF $T4/T1$ (40mA or adequate to achieve TOF response while comfortable for the patient) within 15min of PACU arrival and hourly until up to 3h after the end of surgery or sooner if the patient meets PACU discharge criteria. We will record the initial PACU TOF and calculate the PACU average TOF. After transfer to the postoperative floor, the blinded investigator will assess residual or recurrent NMB with the qTOF monitor twice a day, with 3 repetitions each time, and each assessment separated by ≥ 6 h. This will be maintained for up to 3 days after the end of surgery or until end of monitoring criteria are met.
- The individual doses of administered opioids received by the patient during the study (PACU and daily for up to 3 postoperative days or until the end of monitoring criteria are met) will be recorded and converted to morphine equivalents[21] to statistically evaluate the effect of opioid administration on hypoventilation events.
- Nursingcharted episodes of respiratory depression during the PACU stay will also be recorded. Postoperative pulmonary complications (as defined elsewhere[13]) during PACU and up to 3 postoperative days will be collected.

Postoperative end of study follow-up

At postoperative day 14 ± 3 during the patient's visit to the transplant surgery clinic or via a phone call, the PROMIS® Dyspnea Functional Limitations Short Form questionnaire will be repeated

and normalized to the patient's baseline. Any postoperative pulmonary complications[13] and hospital resources utilization occurring from the hospital discharge until this end of study follow-up will be collected from the patient and the medical record, and the estimated costs based on average hospital daily stay depending on type of care unit or reported cost of complications calculated.

Any signs and symptoms of hypersensitivity (e.g. rash, anaphylaxis) detected during PACU and up to 3 postoperative days will be collected from the patient and patient's providers. The relationship of these signs and symptoms to sugammadex will be assessed by the patient's providers and also by the study safety officer. Their confirmatory diagnostic testing and management will be performed at the discretion of the patient's providers.

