Incidence of residual or recurrent NMB in the postoperative floor. This will be calculated as described before (T4/T1 <0.9 , considered severe if T4/T1 <0.4), as an average of 3 repetitions obtained on two occasions separated by ≥ 6 h daily on postoperative days 1-3 or until the end of monitoring criteria have been met.

Morphine equivalents will be calculated from individual opioid doses administered to each patient following standard conversion formulas[21, 40]. This morphine equivalent dose will be calculated for the PACU period and daily for 3 first postoperative days or until the end of monitoring criteria have been met, and used as covariate in the logistic regression analysis.

Time from NMBR administration to quantitative TOF T4/T1 >0.9 (minutes, one decimal). The quantitative TOF will be repeated at 80 mA every 30 seconds from the moment the NMBR medication (sugammadex or neostigmine) has been completely administered intravenously.

Time from NMBR administration to extubation (minutes, once decimal).

Time of total operating room time (minutes), counting from in-room time stamp to out-of-room time stamp.

The PROMIS® v1.0 Dyspnea Functional Limitations Short Form 10a_9-2-2016 questionnaire is a validated and standardized short questionnaire to quantitate if sugammadex used for NMBR reduces the subjective dyspnea scores relative to baseline. It will be completed by the patient in the preoperative phase and during the postoperative follow up. It is available at http://www.healthmeasures.net/administrator/components/com_instruments/uploads/PROMIS%20SF%20v1.0-Dyspnea%20Functional%20Limitations%2010a_9-2-2016.pdf.

Postoperative Pulmonary Complications (PPCs) following previous definitions[13, 41, 42], including:

Respiratory Failure, defined as[41]: "When postoperative $\text{PaO}_2 < 60\text{mmHg}$ on room air, a ratio of PaO_2 to inspired oxygen fraction < 300 or arterial oxyhemoglobin saturation measured with pulse oximetry (SpO_2) $< 90\%$ and requiring oxygen therapy".

Unplanned intubation with postoperative mechanical ventilation (POMV), defined as placement of a breathing tube that was not intended or planned, excluding instances of intubation during an unplanned return to the operating room. Also excluded those patients that were transferred intubated and ventilated to the intensive care unit (ICU) from the operating room.

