Kidney graft outcomes, including postoperative ClCr, daily urine output, need for dialysis postoperatively, diagnosis of delayed graft function, kidney graft rejection. Postoperative hemodialysis is not usually planned and typically reserved for patients with immediate donor graft failure who exhibit signs of congestive heart failure within the first week after transplantation. The need of rescue hemodialysis within the first week after kidney transplantation is an accepted and simple definition of delayed kidney graft function[46].

Hospital resources utilization: hospital floor length of stay (LOS) (days, rounded to half a day), ICU admission and LOS, estimated cost based on average daily cost at a postoperative UCH floor or ICU and/or based on reported estimated costs per PPC[47, 48]

Hypersensitivity adverse events: hypersensitivity signs and symptoms, including but not limited to rash, bronchospasm or anaphylaxis, will be obtained for up to 3 postoperative days directly from the patient and the patient's providers. Their relationship to sugammadex will be assessed by the patient's physicians and the study safety officer. Their confirmatory testing and management will be performed strictly at the discretion of the patient's physicians.

Statistical Methods

The primary hypothesis is that the frequency of patients with one or more episodes of hypoventilation events in PACU (% of patients) is lower in the sugammadex group compared to neostigmine (controls). This will be analyzed by logistic regression which includes as covariates group allocation, total morphine equivalents, and TOF T4/T1 response, and other observed significant and clinically relevant differences between the groups. The odds ratio for the group covariate will be the primary outcome of interest, with the other covariates included in the model to adjust for potential confounders related to hypoventilation.

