The secondary analysis comparing delayed efficacy of sugammadex to neostigmine in reducing the incidence of hypoventilation during the first 3 postoperative days will assume the same model and covariates as the primary hypothesis. To compare the incidence of PPCs a logistic regression model will be used with the binary outcome of any PPC and will include covariates for group and total morphine equivalents. Hospital length of stay and costs will be compared between groups using a linear regression model including covariates for group, total morphine equivalents, presence of respiratory comorbidities and other clinical differences that may influence the outcome. Continuous outcomes may be transformed if they violate the normality assumption (e.g., a log-transformation).

Multiplicity

Given only one primary outcome and hypothesis, there is a not a concern for multiplicity. Secondary analyses are considered exploratory in this protocol.

Power/Sample Size:

Based upon a sample size of 40 patients per group, this study has 90% power to detect a 50% difference in hypoventilation incidence in the PACU (from 76% as reported in previous studies[21] to 38%, alpha 0.05), assuming a potential dropout of up to 6 patients per group. The 50% reduction is considered clinically relevant for a decrease in the frequency of hypoventilation, a precursor of more clinically significant complications such as hypoxemia, reintubation or pneumonia. Quantifying the contribution of hypoventilation into more severe complications is challenging, and details of duration and severity of hypoventilation are not well known. Thus, only a significant reduction in hypoventilation incidence (i.e. 50%) may be accepted as relevant. This trial will provide additional detailed information that may provide more insight on the clinical consequences of hypoventilation (e.g. potential association between accumulated minutes of MV <40% expMV and decrease in SpO₂/FiO₂ over the following 30 min).

A sample size of 40 patients per group would also have approximately 80% power (78%) to detect a difference in case the incidence of any hypoventilation events is 60%, instead of the literature-based 76%. The table below provides the sample size per group to achieve a variety of assumptions for the primary outcome, alpha, and power:

Incidence Group 1	Incidence Group 2	Alpha	Power	Sample Size per Group
1. 0.76	2. 0.38	3. 0.01	4. 0.8	5. 39
6. 0.76	7. 0.38	8. 0.05	9. 0.8	10. 26

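### The cost outcome omits the reversal drugs being compared and does not cost operating room minutes, and two sections join its two costing methods differently

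*Combined protocol and SAP*

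**What the plan says.** The additional secondary objectives include testing whether sugammadex, compared with neostigmine, "reduces hospital resources utilization (i.e. hospital length of stay, ICU admission) and estimated healthcare costs". Cost is then defined in two places:

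- Section III.F, Variables/Time Points of Interest, under hospital resources utilization: "estimated cost based on average daily cost at a postoperative UCH floor or ICU and/or based on reported estimated costs per PPC[47, 48".
- Section III.C, Postoperative end of study follow-up: "the estimated costs based on average hospital daily stay depending on type of care unit or reported cost of complications calculated".

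Statistical Methods supplies only the analysis: "Hospital length of stay and costs will be compared between groups using a linear regression model", adjusted for group, opioid dose, respiratory comorbidity and other clinical differences. It adds no cost component. The Multiplicity paragraph labels all secondary analyses exploratory.

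Two resources appear elsewhere but in no cost statement. The first is the randomised treatment itself, "NMBR with either sugammadex (intervention group) or neostigmine (control group", with a second drug in the control arm: "Neostigmine will be administered simultaneously with the appropriate glycopyrrolate dose". The second is theatre time, which is an outcome in its own right: "Time of total operating room time (minutes), counting from in-room time stamp to out-of-room time stamp".

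**The concern.** The question is whether choosing one reversal regimen over the other lowers cost. The one resource certain to differ between the arms is the regimen, and the rule does not price it. Operating room time is a second resource that the choice of drug may affect, and it is not priced either. What remains restates length of stay and pulmonary complications (PPCs) in currency. A result reported as a saving in healthcare cost would be silent on the drug bill.

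There is also an ambiguity in how the two listed methods combine. The follow-up section offers them as alternatives, while the variables section also allows both. Neither says which applies to which patient, so bed-day cost, published PPC cost, or their sum could each be presented as the planned analysis. If both were applied to one stay, days added by a PPC might be charged once as bed-days and again within the published cost.

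**Working it through.** The documents state no unit cost, cost difference or power for cost, so there is no figure to reproduce. The check is a comparison of the text plus simple cost algebra.

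**1. Which components are counted**

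| Resource | Recorded? | In the cost rule? |
|---|---|---|
| Floor and ICU days | Yes (III.F) | Yes |
| PPCs | Yes (III.C, III.F) | Yes, through published costs |
| Sugammadex, neostigmine, glycopyrrolate | Given by arm (Intraoperative phase); doses not among the items listed for recording there | No |
| Operating room minutes | Yes (III.A, III.C, III.F) | No |

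**2. Effect of the omission on the arm difference**

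Take all differences as sugammadex minus neostigmine, as means per patient. Let ΔF and ΔI be the differences in floor and ICU days, f and u their daily costs, D the difference in reversal-regimen cost, m the operating room minutes saved with sugammadex, and r the cost per minute.

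- Bed-day costing as planned: f × ΔF + u × ΔI.
- With the missing items: f × ΔF + u × ΔI + D − m × r.
- Discrepancy: D − m × r.

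Linear regression is linear in the outcome. On the untransformed scale, with the same covariates, the group coefficient therefore shifts by the adjusted version of this term, and covariate adjustment does not recover it.

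For an illustration, use one average floor day as the unit. All of these values are assumptions: D from 0.02 to 0.10 (taken as positive, although the documents give no prices), m from 0 to 20 minutes, r from 0.01 to 0.02 per minute.

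- Upper end: 0.10 − 0 × r = +0.10 floor-days per patient.
- Lower end: 0.02 − 20 × 0.02 = −0.38 floor-days per patient.
- Break-even, for example: D = 0.05 and r = 0.01 give zero at m = 0.05 / 0.01 = 5 minutes.

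The sign changes within the range.

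**3. Effect if the two methods were added**

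Suppose a PPC adds k days, valued at k, and the published cost per PPC is L, of which a share s is hospital stay. Adding both charges k + L. Without overlap the charge would be k + (1 − s) × L. Assuming L = k, the ratio is 2 / (2 − s):

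- s = 0: 1.00
- s = 0.5: 2 / 1.5 = 1.33
- s = 1: 2.00

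The arm difference is distorted by the difference in PPC rates × s × L. With s = 1, L = k and assumed rates:

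- 20% vs 10%, k = 1: 0.10 × 1 = 0.10 floor-days per patient.
- 40% vs 20%, k = 5: 0.20 × 5 = 1.00 floor-days per patient.

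The distortion is zero if s = 0 or if only one method is used. It raises the apparent cost of whichever arm has more PPCs.

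**The case against.** The strongest defence is that little rests on this outcome. It is exploratory and described as an estimate, and the Clinical Hypotheses section says that testing such effects would need a much larger trial. The outcome list in III.A can be read as costing only the resource items it names, such as stay and ICU admission, and a hospital-stay perspective is a legitimate choice. That limits the importance of the point. It does not justify the label: the objectives speak of healthcare costs, which a stay-only measure cannot address when it leaves out the treatments compared.

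Several stronger readings are tempting, and the documents do not support them.

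- *The omission favours sugammadex.* No prices are given, and any operating room saving works against a higher drug cost, so the net sign is open.
- *Every patient's cost is wrong by the same amount.* Doses are per kilogram and vary with twitch recovery, and each patient receives one regimen. Only a mean gap can be stated.
- *Operating room time differs by arm.* The Background describes neostigmine reversal as slower in the general population, but total room time in this trial is an outcome still to be observed.
- *A theatre-time saving would go unseen.* It would be reported in minutes; it is only left out of the cost.
- *The plan double counts complications.* That requires the additive reading of III.F and published costs that include stay. III.C says 'or'. One cited source has a title that mentions hospital stay, but its cost content cannot be checked here. Per-PPC costs might also be meant for complications after discharge with no inpatient days, though the protocol does not say so.

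**Conclusion.** The point holds as a limited defect. Followed as written, the costing rule excludes the acquisition cost of the randomised regimens and assigns no cost to operating room minutes, so it cannot answer the stated cost question. The size of the gap is D − m × r per patient; its value and direction are unknown without prices and the observed minutes. The figures of +0.10 to −0.38 floor-days rest wholly on assumed inputs.

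The mismatch between 'or' and 'and/or' is plain in the text and needs reconciling. Double counting is only a possibility, with a per-PPC factor between 1.00 and 2.00 under the assumption that the published cost equals the value of the added days. The primary outcome, its analysis and the sample size are untouched.

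**What to change.** Define one per-patient cost in the analysis plan before unblinding:

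cost = (reversal and anticholinergic dose given × unit price) + (operating room minutes × unit cost) + (floor days × daily cost) + (ICU days × daily cost).

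Reconcile the follow-up and variables sections so that published per-PPC costs serve only as an alternative sensitivity analysis and are never added to bed-day cost for the same stay.

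If the sponsor prefers to keep the present ingredients, label the outcome as postoperative stay cost and draw no conclusion about healthcare cost.

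The change costs some plan wording, a local unit price list and retrieval of the reversal doses actually given, which the Intraoperative phase does not list among the items to record. Operating room minutes are already collected. No patient procedure changes.

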- **Insufficient neuromuscular blockade reversal (NMBR):** Insufficient neuromuscular blockade reversal at the end of surgery can lead to postoperative complications related to neuromuscular weakness. Complications due to insufficient NMBR range from mild subjective sensation of muscle weakness and up to respiratory failure requiring reintubation and mechanical ventilation, including problems with swallowing, speech or vision, airway aspiration of gastric contents, hypoventilation and increased requirement of oxygen supplementation and pneumonia. The use of sugammadex in this population with severe

kidney disease has not been sufficiently studied but previous small studies have not observed early or delayed events of insufficient NMBR in patients with severe kidney disease. The long-term goal of this study is to reduce insufficient NMBR after kidney transplant surgery, and its contribution to hypoventilation and other complications.

- **Adverse effects related to NMBR agents, including sugammadex (intervention patients) and neostigmine (control patients):** The most common adverse effects to sugammadex include: nausea, vomiting, pain, hypotension and headache. The most common adverse effects for neostigmine include: salivation, fasciculation, bowel cramps and diarrhea. A recent Cochrane systematic review with meta-analysis and trial sequential analysis found that the overall risk of adverse effects, including residual NMBR, nausea/vomiting and bradycardia is lower for sugammadex than for neostigmine, and the risk of severe adverse reactions is similar after sugammadex and neostigmine[30].
- **Local skin irritation to respiratory volume sensor.** The ExSpiron sensor has three electrode pads to be placed against the patient's skin at the sternal notch, xiphoid and right mid-axillary line at the level of the xiphoid. The risk of this bio-impedance-based monitor is minimum, with some possible irritation of the skin in susceptible patients. This monitor has been used with no adverse events[16-21, 37, 38].

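### Hypersensitivity events are collected in both arms but judged for relationship to sugammadex only, so relatedness to the control reversal drug is not captured

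*Combined protocol and SAP*

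**What the plan says.** Two places deal with hypersensitivity, and they agree with each other.

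- **Section III.C, Postoperative end of study follow-up.** Collection: "Any signs and symptoms of hypersensitivity (e.g. rash, anaphylaxis) detected during PACU and up to 3 postoperative days will be collected". Causality: "The relationship of these signs and symptoms to sugammadex will be assessed by the patient's providers and also by the study safety officer".
- **Section III.F, Variables/Time Points of Interest, Hypersensitivity adverse events.** Collection: the signs and symptoms "will be obtained for up to 3 postoperative days directly from the patient and the patient's providers". Causality: "Their relationship to sugammadex will be assessed by" the treating physicians and the safety officer.

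Elsewhere the protocol treats both reversal agents as carrying risk. Section III.D has an item that begins "Adverse effects related to NMBR agents, including sugammadex (intervention patients) and neostigmine (control patients" and lists common effects of each drug. The NMBR brief protocol in section III.C adds a further drug in the control arm: "Neostigmine will be administered simultaneously with the appropriate glycopyrrolate dose".

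**The concern.** In a randomised double-blind comparison of two drugs, a causality question should be put in the same terms to every patient. Here it names the intervention drug alone. A control patient with a rash is assessed for a reaction to a drug that was not given, and nobody is asked about the drugs that were.

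What is at stake is the safety description. A statement at the end of the trial on drug-related hypersensitivity by arm would set relatedness to the drug received (sugammadex arm) beside relatedness to a drug not received (control arm). The missing judgement could be recovered only by assessing the events again.

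**Working it through.** No figure in the plan bears on this point, so there is none to reproduce. The check is a comparison of the text, followed by one illustration of scale.

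**1. Collection.** Neither section restricts collection by arm. All-cause hypersensitivity can be counted on the same basis in both groups.

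**2. The causal question.** Both sections name sugammadex and no other drug. Because the procedures and the variable definitions agree, this reads as a rule and not as a slip in one sentence.

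**3. Any question about the control drug.** Section III.D lists effects of neostigmine but describes no relatedness assessment. The NMBR brief protocol specifies glycopyrrolate with neostigmine and is silent on attribution. No section asks about a neutral study drug. Rocuronium is not named either, but both arms receive it, so that omission does not separate the arms. Neutral wording already exists in the protocol: the section III.F variable for time from reversal to TOF recovery speaks of the reversal medication and names both drugs in brackets.

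**4. What the rule records.**

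| Assessor | Event in a sugammadex patient | Event in a control patient |
|---|---|---|
| Knows the arm | Relatedness to the drug received | Necessarily unrelated; the drug received is not asked about |
| Does not know the arm | Relatedness to the drug received | Relatedness to a drug not received, possibly positive; the drug received is not asked about |

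In both rows the right-hand cell lacks relatedness to the control drug. The rows differ in whether a positive answer is possible for a control patient.

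**5. Which row applies.** Section III.C, Preoperative phase, says that the PI alone is unblinded. The opening of section III.F gives the group codes to the PI and to a safety review monitor. The documents do not say whether that monitor is the study safety officer who judges hypersensitivity, and they do not state the blinding of the treating physicians. The two assessors may therefore sit in different rows.

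**6. Use in the analysis.** Statistical Methods sets out models for hypoventilation, pulmonary complications, length of stay and costs. It gives none for hypersensitivity or for drug-related events. Multiplicity calls the secondary analyses exploratory.

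**7. Scale.** The documents give no hypersensitivity rate, so the rates below are assumptions. With *n* control patients and a per-patient rate *r*, the chance of at least one control-arm event is 1 − (1 − *r*)^*n*. I use *n* = 50 (the 100 patients in Study Design, assuming an even split) and *n* = 40 (the figure in Power/Sample Size).

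| Assumed *r* | *n* = 40 | *n* = 50 |
|---|---|---|
| 0.1% | 3.9% | 4.9% |
| 0.3% | 11.3% | 13.9% |
| 1% | 33.1% | 39.5% |
| 3% | 70.4% | 78.2% |

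For example, 1 − 0.99^50 = 0.395. Depending on the rate, the gap may affect no control-arm event at all, or it may well affect at least one.

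**The case against.** The strongest reply is that nothing planned depends on this judgement. The comparison that randomisation supports is all-cause incidence by arm, and that remains available. This stands, and it keeps the point minor.

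The protocol also mentions an independent safety review and regulatory communication of adverse events, without giving their content. Control-drug causality might be considered there. That also stands as a caution: the text shows only that the hypersensitivity assessment names one drug and that no section provides for the other.

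A reader might go further and infer four things that the documents do not support.

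- *The control arm has no relatedness data.* The sentence covers every collected event, so control patients are assessed too. What is missing is relatedness to their own reversal drug.
- *Related events in the control arm are zero by construction.* That holds only if every assessor knows the arm. A blinded assessor may judge a control patient's event related to sugammadex.
- *The planned safety comparison is biased.* No relatedness-based comparison is planned.
- *The wording drives blinded providers to seek the allocation.* Neither section asks them to obtain it, and the codes are restricted. A causality question about either drug could prompt the same curiosity.

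**Conclusion.** The point holds as a minor defect in what is recorded. Followed as written, the rule yields no judgement of relatedness to neostigmine with glycopyrrolate, and a count of drug-related hypersensitivity would not mean the same thing in the two arms. This does not depend on whether the assessors are blinded. It does assume that the hypersensitivity item is applied literally and that the safety processes whose content is not described do not supply the missing judgement.

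Its size in events cannot be stated, for want of a rate. It has no effect on all-cause incidence, on the primary outcome or on any specified model.

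**What to change.** - In section III.C (Postoperative end of study follow-up) and section III.F (Hypersensitivity adverse events), replace sugammadex in the causality sentence with: the study reversal drug (sugammadex or neostigmine/glycopyrrolate).
- State that the same assessment is applied in both arms and that the patient's physicians record their relatedness judgement without knowledge of allocation.
- State whether the study safety officer is the safety review monitor who holds the group codes. If so, say that this second judgement is made with the codes available. A requirement that all assessors be blinded would otherwise conflict with the opening of section III.F.
- Name all-cause hypersensitivity by arm as the main summary, with relatedness as supporting description.

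The cost is minor rewording of the protocol and the adverse-event form, with no new visit or test. Any events already judged under the current text would need a second relatedness assessment. Diagnostic testing and management of reactions are not affected.
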